7 PHARMACOKINETICS AND STATISTICAL CONSIDERATIONS

7.1 Study Hypotheses

Due to differences in inactive ingredients between reference and generic fentanyl transdermal patches the release rate of fentanyl may differ from these patches upon exposure to heat. As a result, in this study the influence of standardized heat application (two heat periods) on the pharmacokinetics (PK) parameters of fentanyl will be studied after using Duragesic[®] (reference), Apotex (fentanyl) (generic), and Mylan (fentanyl) (generic) transdermal patches.

The primary analysis will be to determine whether heat differentially impacts fentanyl serum concentrations among Duragesic[®] (reference), Apotex (fentanyl), and Mylan (fentanyl) transdermal patches. We will test the null hypothesis (H₀) that the coefficient for the patch-by-heat interaction equals zero, adjusting for time.

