7.3 Final Analysis Plan

The main objective of this study is to investigate the influence of heat application on the PK parameters of fentanyl after using reference and generic patch products. The primary PK parameters to be compared are 1) Cmax, before and after heat application and 2) AUC before and after heat application consistent with similar PK studies [4, 5, 7, 8, 16-22]. Analysis of variance (ANOVA) followed by post-hoc Bonferroni test will be used for comparing the differences in the means of the PK parameters and significant differences will be declared at p < 0.05. The statistical comparisons will be conducted as follow:

Three pair-wise comparisons between the patches (Apotex v Mylan; Apotex v Duragesic[®]; and Mylan v Duragesic[®]) will be performed using the results of a three-way repeated-measures ANOVA. The model will include time, type of patch (e.g., Apotex or Mylan), application of heat (yes or no), and interaction between patch and application of heat. The time term comprises multiple indicator variables for maximum model flexibility to perform the comparison at different time points specified above. We will test the null hypothesis that the coefficient for the patch-by-heat interaction equals zero, adjusting for time.

If fentanyl concentrations are found to be non-normally distributed, then we will examine Box-Cox transformations (e.g., log, square-root, etc.) that can achieve normality. If no transformation can achieve normality, then we will use permutation tests to compute empirical p-values, and we will use the bootstrap to compute standard errors and confidence intervals that account for within-person correlation.

A secondary analysis will assess the effects of heat and time on fentanyl within a patch. Specifically, the ANOVA will also include interaction terms of time with patch and heat, and a three-way interaction between time, heat, and patch. Inclusion of the three-way term allows the effects of heat on fentanyl to differ by patch. Testing the time-by-heat interaction, separately for each patch, using the same procedure outlined above produces estimates of intra-procedure effects.

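### The primary patch-by-heat model forces one time curve on all patches and leaves heat coding and error term open, so its level, power and even sign depend on unstated choices

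*Combined protocol and SAP*

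**What the plan says.** Section 7.1 of the combined protocol and SAP states: "The primary analysis will be to determine whether heat differentially impacts fentanyl serum concentrations among" the three products. It adds: "We will test the null hypothesis (H₀) that the coefficient for the patch-by-heat interaction equals zero, adjusting for time". Section 7.3 says that the three pairwise patch comparisons "will be performed using the results of a three-way repeated-measures ANOVA". On the terms it says: "The model will include time, type of patch (e.g., Apotex or Mylan), application of heat (yes or no", together with a patch-by-heat term. On time: "The time term comprises multiple indicator variables for maximum model flexibility". Interactions with time appear only in the secondary analysis. Within-person correlation is mentioned only for the bootstrap, which is a fallback if no transformation gives normality.

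The same section also says: "The primary PK parameters to be compared are 1) Cmax, before and after heat application and 2) AUC before and after heat application". The response is therefore concentrations in one place and interval PK parameters in another.

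Section 4 gives each product two procedure days, one with heat at 11-12 h and one at 18-19 h. No day is unheated. Nothing in 7.1 to 7.3 says which samples count as heated, or names a covariance structure, an error stratum or a session term. The separate SAP document deals with the in vitro-in vivo correlation and adds nothing on this model.

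**The concern.** Three features interact.

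- **One time curve.** With shared time indicators and no time-by-patch term, the products may differ only by a constant shift plus the heat term. Section 3.1 itself expects absorption kinetics to vary between patch designs.
- **No clean control for late heat.** If heat means the heated hour, every sample after that hour counts as unheated. The 18-19 h controls for the late-heat session are then samples from a session already heated at 11-12 h.
- **No stated error term.** Each subject gives six sessions of closely spaced samples. If residuals are taken as independent after a subject term, between-session variation inflates the residual, while serial correlation makes the samples look more informative than they are. These push the test level in opposite directions.

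At stake is the trial's main question: whether a generic patch responds more to heat than the reference. The test could miss a real difference, declare a false one, or rank the more heat-sensitive product as the less sensitive.

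**Working it through.** Sections 7.1 to 7.3 give no variance, correlation or expected heat effect, so there is no planned figure to reproduce.

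**1. Layout (sampling list in 7.2).** One pre-patch and 23 later samples make 24 per session, 24 x 6 = 144 per subject and 1,440 in all. Under heated-hour coding, six times (11:05 to 12:00) are heated in the early-heat session and six (18:05 to 19:00) in the late-heat session. Of 24 x 2 x 3 = 144 time-by-heat-by-patch cells, the 12 times outside the heat hours leave 12 x 3 = 36 empty. The other 12 times are fully crossed.

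**2. Common curve.** Before application no product has delivered any drug, so a constant shift between products cannot hold both there and later. The SAP lists bioavailabilities of 0.36, 0.39 and 0.42. With those levels, assumed different onset rates and equal heat ratios, the heated-hour model with subject effects rejected in 26-76% of trials. Part of this comes from the raw scale, where equal ratios give unequal absolute rises.

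**3. Carry-over (half-life about 24 h, section 4; single-exponential decline assumed).** Set the extra concentration at the end of the heated hour to 1. It rises almost linearly, so the six samples average (5+15+25+35+45+60)/360 = 0.514. In the early-heat session the part remaining at time t is 2^(-(t-12)/24): 0.84 at 18:05, 0.82 at 19:00, mean 0.829.

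- Heated minus unheated at 11-12 h: 0.514 - 0 = 0.514.
- Heated minus unheated at 18-19 h: 0.514 - 0.829 = -0.315.
- Average: (0.514 - 0.315)/2 = 0.10. Least squares with the 7.3 terms on noise-free curves at all 24 times gives 0.11.
- With a 15-minute delay from heat to serum: (0+0+10+20+30+45)/360 = 0.292 and carry-over 0.835, so (0.292 + 0.292 - 0.835)/2 = -0.13. The full fit gives -0.12. The sign is reversed.
- If the extra concentration instead decays with a 2 h half-life (assumed), carry-over averages 0.105 and the contrast is (0.514 + 0.514 - 0.105)/2 = 0.46, largely intact.

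With zero-order input after a 2 h lag and no delay, the late-to-early session ratio at 18-19 h is 0.99 for 1.5-fold and 0.94 for 4-fold heated input. The session being heated has the lower concentrations.

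**4. Simulation (n = 10, protocol times, 2 h lag, 24 h half-life; all variances assumed).** Power is for heated input of 4-fold in one product and 1.5-fold in the others.

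| Analysis | Type I error | Power |
|---|---|---|
| Heated hour, subject term, independent residuals | 0.7-4% (session CV 5-25%, residual SD 5%, 10-minute correlation 0.8); 31-37% (correlation 0.9, SD 15%, session CV 5%) | 3-18% |
| Subject x patch x heat stratum | 3.8-5.5% when curves agree; 19-22% with input lags of 1, 2 and 4 h | 5-52% |
| Early-heat log contrast, 12:00-17:55, pre-heat corrected | 4-7% | 100% (residual SD 5%) |

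Restricted to the heat window, with residual SD 10%, an early-heat log contrast had power of 65-69% at 4-fold and 29-33% at 3-fold.

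**5. A second model (heat effect decaying with a 2 h half-life; subject/session/within-session CV from 30/15/10% to 50/40/30%; correlation 0.9 per hour).** Rejection under the null was 1-18% for heated-hour coding with subject effects, 15-66% when heat is coded from onset onward, and 56-87% when coded by session type. For heat ratios 1.5/1.5/2.0, heated-hour coding with subject effects had power of 61-100% with no lag. With a 30-minute lag, heated-hour coding had 0-5%. A subject-level log contrast of early-session post-heat Cmax had 68-100% and 53-99.5%, with type I error of 4-8%.

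**The case against.** The strongest defence is that the plan says repeated-measures ANOVA and nowhere says that samples are independent. A reader might infer that it treats the serial samples as exchangeable and that its standard errors are simply wrong. The documents do not support that: the error term is open, and the poor error rates belong to one way of filling the gap.

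A reader might also infer that the 36 empty cells rule out a classical analysis. They do not. The 12 crossed times support a subject x patch x heat error term, in which additive session effects cancel. It held 3.8-5.5% even in the variance mix where independent residuals gave 31-37%. This stands. It does not restore power, because the weakness there is the carry-over in the control samples rather than the error bars, and its level rests on the curves agreeing.

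The Cmax and AUC reading also stands as possible, and there the serial samples do not enter as separate observations. However, 7.1 names concentrations, and the time indicators and normality check in 7.3 fit concentrations. A between-session comparison of Cmax or AUC over 18-19 h would meet the same carry-over.

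Finally, low power is not general. With fast decay and no lag, the heated-hour model performs well.

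**Conclusion.** The point holds as a serious gap in the primary analysis, not as a proven error in its standard errors. On the documents alone, the primary model imposes a common time curve, does not define heat for a design in which every session is heated, and states no session term, serial correlation or error stratum. Under heated-hour coding with independent residuals after a subject term, the test can be far too conservative, far too liberal, or of the wrong sign. The error stratum cures the level when curves agree, but power can remain as low as 5% for a 4-fold against 1.5-fold difference in heated input.

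All error rates and powers rest on assumed variances, correlations and heat-response shapes. The carry-over figure rests on the protocol's 24 h half-life and a single-exponential decline; a much faster decline would largely remove it. A primary test that depends this much on unstated choices should be settled in the SAP before analysis.

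**What to change.** Make the primary analysis one log heat-response value per subject and product:

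1. In the early-heat session, take log AUC (or log Cmax) over a fixed window starting at 11 h and ending before 18 h (last sample 17:55). Subtract the log of that session's own pre-heat level, the mean of the 10:00 and 10:55 samples.
2. Compute the same quantity over the same clock window in the late-heat session, which is still unheated then, and subtract it.
3. Compare the three products on the 10 x 3 values, with F on 3 - 1 = 2 and (10 - 1)(3 - 1) = 18 df, then the three pairs at 0.05/3 = 0.0167.
4. Report the late heat period separately, as a secondary within-session contrast against the 17:00 and 17:55 samples, because the early-heat session is not an unheated control at 18-19 h.

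Alternatively, fit a mixed model with time-by-patch terms, subject, subject-by-product and session effects, serially correlated residuals, and heat coded to include the post-heat period. Either way, state the response variable and which samples count as heated.

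The cost is SAP wording and reprogramming, with no new samples. The price is that the primary test then uses only the early heat period, and the plan should say so.

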3.2 Study Outcome Measures

The main outcome measure of the study is the measurement of maximum serum concentration (Cmax); time of maximum serum concentration (Tmax) of fentanyl and area under the curve (AUC) attained with and without heating in each of the three fentanyl patches (reference and generic).

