4 STUDY DESIGN

This is an open-label, non-placebo controlled pharmacokinetic (PK) assessment study. The study will consist of six-procedure days (10 subjects) with at least two weeks between procedure days. The half-life of fentanyl is approximately 24 hours. Hence, 7 days (i.e. 5 half-lives) will be sufficient for >95% of fentanyl to be eliminated from the body. Each of the 10 subjects will be enrolled to complete all six procedure days (Procedure Days 1 to 6). The study is open label and not blinded, because PK assessment is not subject to participant and/or observer bias. After each procedure session (procedure day) is completed, the available safety data will be reviewed by an Independent Safety Monitor (ISM) to determine whether or not to proceed to the next procedure day.

The six procedures days are as follows:

Procedure Day 1: An **Apotex** (fentanyl) patch will be applied without heat for 11 hours, then a theratherm® heating pad will be applied over it (see details in Manual of Procedures) and set to induce a skin temperature of $42.0 \pm 2^{\circ}$ C for 1 hour then removed, and the patch will be kept on for another 7 hours (patch will be applied for a total of 19 hours), then it will be removed. Each subject will receive a naltrexone hydrochloride 50 mg oral tablet 12 ± 1 hour and shortly prior to patch application and then every 12 ± 1 hour for 8 additional doses, then one dose every 24 ± 2 hours for two more doses. A total of twelve 50 mg oral doses of naltrexone will be administered.

Procedure Day 2: An **Apotex** (fentanyl) patch will be applied without heat for 18 hours, then a theratherm® heating pad will be applied over it and set to induce a skin temperature of $42.0 \pm 2^{\circ}$ C for 1 hour, then the patch and the heating pad will both be removed (patch will be applied for a total of 19 hours). Each subject will receive a naltrexone hydrochloride 50 mg oral tablet 12 \pm 1 hour and shortly prior to patch application and then every 12 ± 1 hour for 8 additional doses, then one dose every 24 ± 2 hours for two more doses. A total of twelve 50 mg oral doses of naltrexone will be administered.

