7.2 Pharmacokinetics (PK) Analyses

Fentanyl concentrations will be measured in serum samples collected from each subject from the opposite arm to which the fentanyl system will be applied. Blood samples (approximately 5 mL) will be collected during each procedure day, 15 min before patch application and then at 1:00, 10:00, 10:55, 11:05, 11:15, 11:25, 11:35, 11:45, 12:00, 13:00, 14:00, 16:00, 17:00, 17:55, 18:05, 18:15, 18:25, 18:35, 18:45, 19:00 20:00, 21:00 and 22:00 hr post-patch application. The fentanyl PK parameters to be estimated using non-compartmental analysis (NCA) after each system application are: maximum serum concentration (Cmax) at different time intervals; 0-11, 0-19, 0-22, 11-12, 12-18, 18-19 and 19-22 hr; apparent elimination rate constant (k); apparent half-life (t1/2), calculated as 0.693/k; AUC of the serum concentration–time at different time intervals; 0-11, 0-19, 0-22, 11-12, 12-18, 18-19 and 19-22 hr determined by the linear trapezoidal method; and AUC value extrapolated to infinity (AUCinf), calculated as the sum of AUC₂₂ and the area extrapolated to infinity: AUCinf = AUC₂₂ + C₂₂/k where C₂₂ would be the last quantifiable concentration. All NCA analyses will be conducted using Phoenix® WinNonlin[®] 6.3 (Pharsight, a Certara Company, CA).

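### The primary patch-by-heat test uses a yes/no heat term that is not defined by sample, and either natural coding mixes during-heat, post-heat and not-yet-heated samples

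*Combined protocol and SAP*

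**What the plan says.** - **Primary test.** Section 7.3 lists the model terms as time, patch, "application of heat (yes or no), and interaction between patch and application of heat". It then states: "We will test the null hypothesis that the coefficient for the patch-by-heat interaction equals zero, adjusting for time". Section 7.1 sets the same null hypothesis and describes the subject of study as "the influence of standardized heat application (two heat periods").
- **Sessions.** Section 4 gives each product two sessions. In the early session the pad is on at 11–12 h. In the late session the "patch will be applied without heat for 18 hours" and is then heated at 18–19 h. No session is unheated throughout, although section 3.2 speaks of Cmax, Tmax and AUC "attained with and without heating in each of the three fentanyl patches".
- **Sampling.** Section 7.2 has 24 samples per session, among them "13:00, 14:00, 16:00, 17:00, 17:55, 18:05". Its intervals for Cmax and AUC are "0-11, 0-19, 0-22, 11-12, 12-18, 18-19 and 19-22 hr".
- **Secondary analysis.** Section 7.3 adds "interaction terms of time with patch and heat, and a three-way interaction between time, heat, and patch". It uses the same heat indicator and does not define it.
- **SAP, IVIVC.** Step 1 of Approaches II and III builds a 32°C baseline from the unheated parts of the early and late profiles. It does not say whether early-session samples after heating belong to it.

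**The concern.** Because every session is heated once, heat cannot be a session label. It has to change within a session, and the primary coefficient then depends on how samples after pad removal are classed. The available text does not class them. Two analysts could follow section 7.3 faithfully and estimate different quantities, and the choice could be made after the data are seen.

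A two-level term also has to describe three states: not yet heated, pad on, and post heat. If extra drug from the heat hour persists, the post-heat samples belong with neither of the other two. The primary question is whether the products respond differently to heat, and section 2.2 intends the answer to support policy on generics. A coefficient whose meaning depends on an unstated rule is a weak basis for that.

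**Working it through.** The plan gives no figure for this test in the available sections, so there is none to reproduce.

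**1. Sample counts (section 7.2 times, section 4 heat hours)**

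| Clock time | Samples | Early session | Late session |
|---|---|---|---|
| Before 11 h | 4 | not yet heated | not yet heated |
| 11:05–12:00 | 6 | pad on | not yet heated |
| 13:00–17:55 | 5 | post heat | not yet heated |
| 18:05–19:00 | 6 | post heat | pad on |
| 20:00–22:00 | 3 | post heat | post heat |

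Per product (48 samples), 12 are pad on and 36 are not. Of those 36, 14 early-session and 3 late-session samples are post heat: 17/36 = 47%. After 18 h the only same-product comparator for late heat is a session heated earlier.

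**2. What each coding estimates**

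Heat has the same pattern in every product and time is common to all. The interaction for two products is therefore the difference between them in (mean of *yes* samples minus mean of *no* samples). Assume equal unheated profiles and equal persistence. Let S be the summed heat excess over the 17 post-heat samples, in units of the mean pad-on excess. As a share of the true during-heat product difference:

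- pad-on coding (12 *yes*, 36 *no*): 1 − S/36
- from-onset coding (29 *yes*, 19 *no*): (12 + S)/29

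The first equals 1 only if S = 0, the second only if S = 17.

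**3. Illustration**

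Assumptions: one compartment, constant input for 0–19 h, input multiplied by H during the heat hour (H = 2, 2.5 and 3 for the three products), raw concentrations, no noise. With k = ln 2/half-life, the excess per unit of extra input is (1 − e^(−ku))/k at u hours after onset (u ≤ 1). Afterwards it decays as e^(−k(u−1)). Only the 24 h half-life is in the documents (section 4, for washout).

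| Half-life (h) | 24 | 7 | 3 | 1 |
|---|---|---|---|---|
| Early, 13:00–17:55 | 8.75 | 6.83 | 4.49 | 1.51 |
| Early, 18:05–19:00 | 9.63 | 6.04 | 2.51 | 0.12 |
| Early, 20:00–22:00 | 4.48 | 2.37 | 0.72 | 0.01 |
| Late, 20:00–22:00 | 5.49 | 4.73 | 3.62 | 1.54 |
| S (sum; last digit may differ by rounding) | 28.35 | 19.97 | 11.34 | 3.19 |
| Pad-on: 1 − S/36 | 0.21 | 0.45 | 0.69 | 0.91 |
| From onset: (12 + S)/29 | 1.39 | 1.10 | 0.80 | 0.52 |

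Least-squares fits of the planned model give the same shares. The late contrast alone is 1 minus the mean early excess at 18:05–19:00 (1.605, 1.006, 0.418, 0.020), which gives −0.61, −0.01, 0.58 and 0.98.

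**4. Unequal persistence**

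The pad-on share is 0.912 at a half-life of 1 h and 0.411 at 8 h.

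- Equal pad-on excess, 8 h versus 1 h: 0.411 − 0.912 = −0.50 of the pad-on effect. An interaction is created.
- 1.5 times the excess at 1 h versus 1.0 at 8 h: (1.5 × 0.912 − 0.411)/0.5 = 1.91. The difference is inflated.
- 1.5 times the excess at 8 h versus 1.0 at 1 h: (1.5 × 0.411 − 0.912)/0.5 = −0.59. The difference is reversed.

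**5. Separating the states**

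With pad-on and post-heat terms each crossed with patch, the same model recovers 1.00 at all four half-lives. So does early minus late at 11:05–12:00, by construction. Pooling all 11 samples from 11:05 to 17:55 does not: (6 + 8.75)/11 = 1.34, then 1.17, 0.95 and 0.68.

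**The case against.** **Size.** The strongest objection is that the size is unknown. The 24 h half-life is a washout figure, and at 1 h pad-on coding loses only about 9%. This stands. Fast clearance does not settle the ambiguity, though: at 1 h the two codings still give 0.91 and 0.52.

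**Response variable.** Section 7.1 speaks of concentrations. Section 7.3 names Cmax and AUC before and after heat as the primary parameters, and its time points may be the section 7.2 intervals. This stands as a limit on the figures. With the five disjoint intervals as response, pad-on coding gives 0.57, 0.68, 0.69 and 0.75 for Cmax and 0.13, 0.37, 0.61 and 0.85 for mean concentration, so that reading does not rescue the plan.

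**Early and late heat are already separated.** The intervals and the secondary time-by-heat terms do distinguish the two heat periods. They do not define the indicator in the primary test, and their 18–19 h contrast still uses an earlier-heated comparator.

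**Stronger readings.** A reader might infer that the primary test is diluted in general and will miss real product differences. That result needs equal persistence across products, which the documents do not state; their premise is that formulations differ. A reader might also infer that the design has no unheated control. It has one until 18 h, in the late session.

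**Missing text.** A definition may exist in material not available here, such as the Manual of Procedures cited in section 4. Section 7.3 should still carry it.

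**Conclusion.** The concern holds as an ill-defined and potentially biased primary estimand. The omission and the sample counts come directly from the text. That neither binary coding recovers the during-heat product difference, except when S happens to equal 0 or 17, follows from the design given equal unheated profiles and equal persistence.

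Dilution is one case. Its size, from 9% to 79% lost under pad-on coding at half-lives of 1 to 24 h, is conditional on a one-compartment model, raw concentrations, equal persistence and no noise. It is not a prediction for this trial. With unequal persistence the direction is open.

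This should be fixed before analysis. It does not invalidate the design, because the samples needed for a clean during-heat contrast are already planned. Nor do the documents support a conclusion that late heat must leave the primary test, since section 7.1 names two heat periods.

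**What to change.** 1. In section 7.3, replace the yes/no term with a pre-specified sample-level factor (not yet heated, pad on, post heat), each level crossed with patch. Keep early and late heat distinguishable, and state the response variable.
2. Include patch-by-time terms or form differences within product. Estimate the during-heat effect as early minus late session at 11:05–12:00, where the late session is an unheated control, and name this as the during-heat estimand. Report 13:00–17:55 as a separate post-heat effect, not pooled with it. The within-product step matters. If the SAP's bioavailability values (0.36 Duragesic, 0.42 Mylan) are assumed to scale the unheated profiles, early-heat terms in the common-time model give a false interaction of 0.42, 0.36, 0.23 and 0.09 of an H = 2 effect at half-lives of 24, 7, 3 and 1 h. Same-product differences give 0.00.
3. Label 18–22 h contrasts as late heat versus an earlier-heated session. Whether late heat stays in the primary test is the sponsor's choice.
4. Separately, in SAP step 1, exclude early-session samples after 11 h from the 32°C baseline and label any baseline after 18 h as model-based. In the illustration with H = 2, the early-session value at 13:00 would be too high by 8.8%, 11.8%, 17.2% and 25.0%.

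**Cost.** No new samples are needed, but precision falls. In per-sample SD units for one subject with no session variance, the pooled pad-on coefficient has standard error √[2(1/12 + 1/36)] = 0.47, and the during-heat contrast √(4/6) = 0.82. Signal-to-noise relative to the pooled test is (0.471/0.816)/share, or 2.72, 1.30, 0.84 and 0.63 at the four half-lives. If session variance equals per-sample variance, the contrast's standard error is 1.21 and the ratios are 1.83, 0.87, 0.57 and 0.43. Power therefore falls if the extra drug clears fast. No observed 32°C baseline remains after 18 h.

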DETERMINATION OF SERUM FENTANYL LEVELS AFTER USING REFERENCE AND GENERIC TRANSDERMAL FENTANYL PATCHES WITH AND WITHOUT STANDARDIZED HEAT APPLICATION IN HEALTHY HUMAN VOLUNTEERS

Short title: The Effect of Heat on Fentanyl Release from Fentanyl Patches in Healthy Adults

Clinical Protocol Principal Investigator:

[name], MS

U01 Principal Investigator(s):

[name] (contact), PhD

[name]

Sponsor:

Food and Drug Administration

Grant Number: 1U01FD004955-01

Protocol Number: HP-00059884

NCT02486016

Version 8.0 12 June 2017

CLINICAL STUDY STATISTICS

IVIVC

For IVIVC, three correlation levels were examined. Level A was selected to use for analysis of the data. Three different (I, II & III) approaches were examined for Level A.

Level A: a point-to point correlation between in vitro and in vivo profiles.

Level B: comparison between in vitro dissolution time and in vivo residence time.

Level C: a single point correlation between in vitro and in vivo parameters (e.g. J_{max} vs. C_{max}).

Approach I: IVPT data, PK-based mathematical equations and in vitro heat effect coefficient (H_i) were used to predict in vivo concentrations.

• Eq. 2 Prediction after TDS removal:

*R*_{in}: Rate of input (mean flux during steady-state in IVPT experiments)

H_i: In vitro heat effect coefficient (composite heat effect during and after heat exposure); ratio of flux values with heat and without heat

CL: Total body clearance obtained from literature/product package information

- k: Elimination rate constant obtained from literature/product package information (k₁: after IV dose; k₂: after TDS dose)
- t: Time after administration of TDS for Eq.1 and time after removal of TDS for Eq. 2

Co: Initial concentration after TDS removal

Approach II and III:

- 1. Reconstruct baseline (32°C) profile by combining the non-heat (32°C) portion of each profile from the early and late heat study designs.
- 2. Deconvolute the in vivo baseline concentration vs time profile using Phoenix®.
- 3. Construct an IVIVC model by plotting the fraction permeated in vitro vs the fraction absorbed in vivo.
- 4. Predict the in vivo fraction absorbed using the IVIVC model and IVPT data.

- 5. Convolute the predicted in vivo fraction absorbed data using Phoenix® to obtain concentration vs time profile
- 6. Apply in vitro heat effect coefficient H_i (Approach II) or the in vivo heat effect coefficient H_{ii} (Approach III) to the predicted in vivo profile.

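### The primary patch-by-heat model omits patch-by-time and does not say which samples are heated, so part of a level gap between products can appear as a difference in heat response

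*Combined protocol and SAP*

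**What the plan says.** Sections 7.1 and 7.3 of the combined protocol and SAP make patch-by-heat the primary test on serum concentrations: "We will test the null hypothesis that the coefficient for the patch-by-heat interaction equals zero, adjusting for time". Besides time, the model contains "type of patch (e.g., Apotex or Mylan), application of heat (yes or no), and interaction between patch and application of heat". Time is categorical and common to all products: "The time term comprises multiple indicator variables for maximum model flexibility to perform the comparison at different time points specified above". Patch-by-time enters only in the secondary analysis, where "the ANOVA will also include interaction terms of time with patch and heat", along with the three-way term.

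The response is untransformed by default: "If fentanyl concentrations are found to be non-normally distributed, then we will examine Box-Cox transformations".

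Under Section 4 every procedure day includes heat, at 11-12 h on Days 1, 3 and 5 and at 18-19 h on Days 2, 4 and 6. There is no wholly unheated day, so heat (yes or no) has to be assigned sample by sample, and the plan gives no rule for this. The wording elsewhere points in different directions:

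- Section 3.2 speaks of parameters "attained with and without heating in each of the three fentanyl patches".
- Section 7.3 says "The primary PK parameters to be compared are 1) Cmax, before and after heat application and 2) AUC before and after heat application".
- The separate SAP, for its in vitro-in vivo work, has "H_i: In vitro heat effect coefficient (composite heat effect during and after heat exposure); ratio of flux values with heat and without heat", and another step there uses the unheated portion of each profile.

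**The concern.** Common time indicators force two products to differ by the same amount at every clock time. If one product runs proportionally higher, its absolute gap instead grows and shrinks with the concentration curve. Heated samples sit at particular points on that curve, so the one remaining product-specific term, patch-by-heat, absorbs part of the gap.

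How much it absorbs depends on which samples are called heated, and that is left open. The scale is also left open: a normality check decides whether the null hypothesis is an equal absolute heat effect (raw) or an equal relative one (log).

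This is the primary test of a study that Section 2.2 says should support policy on heat effects for generic applications. A level difference reported as a heat difference would answer a different question.

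**Working it through.** The plan gives no figure to reproduce, so the check builds its stated model on its own sampling schedule.

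**Inputs from the documents.** The 24 sample times (Section 7.2), the two heat windows and patch removal at 19 h (Section 4), and the model terms (Section 7.3).

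**Assumptions.**
- One-compartment profile with constant input: A(t) = 1 - exp(-k(t - lag)) from the lag to 19 h, zero before and exponential decline after; k = ln 2 / half-life.
- Half-life 3, 6, 12 or 24 h (Section 4 gives about 24 h) and lag 0, 1 or 2 h.
- Comparator level c x A(t), with no heat effect at all. The illustrative c = 0.42/0.36 = 1.167 is the ratio of two bioavailability values in the SAP. It is a ratio of levels only if drug content is equal, which the documents do not give.

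**Formula.** Both products share the same schedule, so the time indicators and the heat main effect cancel in the difference (c - 1)A(t). Patch and patch-by-heat are then fitted to that difference, and least squares gives

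leak = (c - 1) x [mean of A over heated samples - mean of A over unheated samples],

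taken over the 48 samples of the two sessions.

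**Worked case** (half-life 24 h, lag 0; A scaled so that its 11:05-12:00 mean is 1):
- Pad-on coding, all samples: 12 heated, mean 1.232; 36 unheated, mean 1.109. Leak = 0.167 x 0.123 = 2.1%.
- Onset-on coding, all samples: 20 + 9 = 29 heated, mean 1.325; 19 unheated, mean 0.857. Leak = 0.167 x 0.468 = 7.8%.
- Pad-on coding, samples from 10 h on: 1.232 against 1.241. Leak = 0.167 x (-0.009) = -0.15%.
- Pad-on coding, two heated windows only: heated and unheated samples share the same clock times, mean 1.232 each. Leak = 0.

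**Range over all half-lives and lags, c = 1.167** (leak as % of the 11-12 h level):

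| Samples | Pad-on | Onset-on |
|---|---|---|
| All 24 | 2.06 to 2.96 | 2.45 to 9.15 |
| Without pre-dose and 1 h | -0.23 to 1.14 | -0.71 to 5.32 |
| Two heated windows only | 0 | 0.67 to 6.45 |
| Any of these, with patch-by-time | 0 | 0 |

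The leak is linear in c - 1. With all samples, at c = 1.05 it is 0.6% to 0.9% (pad-on) or 0.7% to 2.7% (onset-on); at c = 1.30 it is 3.7% to 5.3% or 4.4% to 16.4%. For comparison, doubling the flux for one hour in the same model raises the 11-12 h mean by about 5% to 12%.

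**Log scale.** For proportional profiles the log difference is the constant log c, which the patch term absorbs, so the leak is 0. If lag differs by 1 to 2 h between products (samples from 10 h on), the log model without patch-by-time gives -0.4% to -0.1% (pad-on) or 1.0% to 4.6% (onset-on). A log scale therefore does not replace patch-by-time.

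**Choice of null.** Suppose heat raises both products by the same ratio. In matched windows the raw interaction is (c - 1) times the reference heat effect: 5%, 16.7% and 30% of it at c = 1.05, 1.167 and 1.30. On logs it is 0.

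**Post-heat samples.** Let flux be tripled for one product and doubled for the other. On logs with patch-by-time, a two-level pad-on coding that leaves post-heat samples as unheated recovers 29% to 75% of the true 11-12 h differential. A separate post-heat level recovers 98% to 113%.

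**The case against.** The strongest reply is that the plan's language favours pad-on coding. Section 4 uses application of heat for the time the pad is in place, and on early-heat days the pad comes off after an hour. Under that coding the leak is small, rests mainly on the pre-dose and 1 h samples, and vanishes in the two heated windows. This stands as to size. It does not settle the coding, because the before-and-after wording in Section 7.3 keeps the wider reading open, although that phrase describes Cmax and AUC and not the model's heat factor.

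The level gap is assumed. Sections 6.1.1 to 6.1.3 give all three patches the same nominal delivery rate, 25 µg/h, and with equal levels and equal curve shapes the no-heat leak is zero. That also stands.

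The secondary analysis already includes patch-by-time. This limits the consequence but does not change the primary test.

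Three stronger readings are tempting, and the documents do not support them:

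- *The untransformed scale is wrong.* With an equal relative heat effect, the raw interaction is a real difference in absolute concentration, which is defensible where the stated worry is safety. The SAP's ratio definition belongs to in vitro flux, not to this ANOVA. The fault is only that the data would choose the scale.
- *The test has an inflated false-positive rate.* A rate would need a coding, an error term and variances that the plan does not state. No error term is named, but a repeated-measures ANOVA conventionally tests a within-subject interaction against its variation between subjects. This is missing detail, not a demonstrated error.
- *The bioavailability values show that the products differ in level by 1.167.* They do not, without drug content.

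**Conclusion.** The concern holds as a specification gap in the primary analysis and should be fixed. As written, the model can assign part of a plain proportional level difference to patch-by-heat when heat has no effect. At an assumed ratio of 1.167 that part is about 2% to 3% of the 11-12 h level under the more natural pad-on coding, close to zero without the two earliest samples, and up to about 9% under onset-on coding. That the leak is zero with patch-by-time does not depend on the assumed profile; the sizes depend on the ratio, the profile and the coding. The scale is a choice of estimand to be made in advance, and neither scale is an error. A reader might infer that the primary test will mislead; the documents support only that it can, to an extent set by choices the plan leaves open.

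**What to change.** Three changes of SAP wording, with no extra samples or subjects:

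1. Include patch-by-time in the primary model.
2. Define heat status by sample time in three levels: unheated, pad-on (after onset, up to and including one hour later) and post-heat. Post-heat samples then do not serve as unheated controls.
3. Fix the primary scale in advance and drop the normality-driven choice. Log concentration is recommended, reported as generic-to-reference ratios of heat ratios with confidence intervals, with the absolute-scale difference as a supportive safety summary.

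Keep both heat periods in the primary analysis, since Section 7.1 specifies two. The early-minus-late contrast for the same product at 11-12 h, where the late-heat session is still unheated, may be added as a supportive analysis. It should not replace the primary test, because it would drop one of the two periods.

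Costs: unquantifiable samples (pre-dose, possibly 1 h) leave a log analysis, and the added terms use degrees of freedom. With 24 times and three products, patch-by-time takes (24 - 1) x (3 - 1) = 46, or 44 without the pre-dose sample, against 10 x 6 x 24 = 1,440 planned (correlated) samples.
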